## 4.1 Inclusion and exclusion criteria

Table 2: Inclusion Criteria

| Nr. | Inclusion Criterion  | Variable  | Values |
|-----|--|-----------|--------|
| 1   | Male and female subjects $\geq 18$ years and $< 65$ years at time of informed consent  | inex_0020 | yes/no |
| 2   | Body weight of $\geq 45$ kilograms (kg) and $\leq 100$ kg and must have a body mass index (BMI) within the range of 16-39.9 kg/m  .at screening. BMI is calculated as Body weight (kg) / [Height (m)]    | inex_0030 | yes/no |
| 3   | Signed and dated informed consent prior to any study-mandated procedure  | inex_0040 | yes/no |
| 4   | Chronic fatigue determined by the Chalder Fatigue Scale at screening   | inex_0050 | yes/no |
| 5   | Diagnosis of chronic fatigue syndrome /myalgic encephalomyelitis (CFS/ME) under the 2003 Canadian Consensus Criteria (CCC) for ME/CFS syndrome and prolonged post-exertional malaise (PEM) including patients with CFS/ME due to Covid-19 (PACS-CFS) at screening. These criteria will be assessed by obtaining clinical histories and using appropriate symptom checklists. | inex_0060 | yes/no |
| 6   | Bell Score $\geq 20$ and $\leq 50$   | inex_0070 | yes/no |

Table 3: Exclusion Criteria

| Nr. | Exclusion Criterion  | Variable  | Values |
|-----|--|-----------|--------|
| 1   | Severe arterial hypotension (systolic BP $< 100$ mmHg, diastolic BP $< 60$ mmHg) at screening  | inex_0080 | yes/no |
| 2   | Moderate to severe renal insufficiency (e.g., estimated glomerular filtration rate $< 40$ mL/min/1.73 m  , calculated by the Cockcroft-Gault formula or similar equation)  | inex_0090 | yes/no |
| 3   | Cardiac insufficiency with an LVEF lower than 40% and/or uncontrolled cardiac arrhythmia   | inex_0100 | yes/no |
| 4   | Coronary heart disease   | inex_0110 | yes/no |
| 5   | Currently medication with ACE inhibitors and unable to switch to another antihypertensive drug class within 2 weeks prior to baseline visit (treatment with ACE inhibitors not allowed within 24 hours prior to immune adsorption)   | inex_0120 | yes/no |
| 6   | Malignant disease within the last 5 years  | inex_0130 | yes/no |
| 7   | Clinically meaningful laboratory abnormalities at screening that would affect subject safety, as determined and documented by the investigator including but not limited to: Abnormal hematology: Hemoglobin $< 8.0$ g/dL, White Blood Cells count $< 2.5/\mu\text{L}$ or $> 12/\mu\text{L}$ , Platelet count $< 100/\mu\text{L}$
Abnormal liver function tests: ASAT/ALAT $> 3 \times$ higher than upper limit of reference (ULN), GGT, alkaline phosphatase $> 3 \times$ ULN, | inex_0140 | yes/no |

|    |  |           |        |
|----|--|-----------|--------|
|    | Total bilirubin > 2.0 mg/dL or PT-INR > 1.5 Note: Any parameter exceeding the above defined ULN should be re-checked once more as soon as possible, and in each case, prior to enrollment/randomization, to rule out lab error.          |           |        |
| 8  | Any comorbidity bearing risk that patient might not tolerate treatment as judged by investigator   | inex_0150 | yes/no |
| 9  | Medical, psychiatric or other conditions rendering patient incapable to understand the patient information and to give informed consent and maintain compliance during the trial   | inex_0160 | yes/no |
| 10 | Fatigue duration for more than 5 years   | inex_0170 | yes/no |
| 11 | Patients unwilling to have pseudonymized data recorded, analyzed and anonymously published   | inex_0180 | yes/no |
| 12 | Participation in another clinical interventional trial within the last 6 months (or five half-lives, if longer than 6 months) previous to informed consent   | inex_0190 | yes/no |
| 13 | Any surgical procedure requiring general anesthesia within 3 months prior to screening, or planned elective surgery during the study   | inex_0200 | yes/no |
| 14 | Inmates of prisons or patients in psychiatric wards, or other state institutions   | inex_0210 | yes/no |
| 15 | Employee of the Sponsor, investigator or study site  | inex_0220 | yes/no |
| 16 | Patient unable or unwilling to comply with study restrictions or procedures as described in Section 4.   | inex_0230 | yes/no |
| 17 | Patient with known substance abuse or drug dependence currently or within one year prior to study participation, excluding nicotine and caffeine. This is determined through clinical history at screening.                              | inex_0240 | yes/no |
| 18 | Acute critical illness (intubation, ongoing Intensive Care Unit stay at the point of study involvement)  | inex_0250 | yes/no |
| 19 | Acute or severe psychiatric disease (such as dementia, eating disorders, major unstable depression, bipolar affective disorder, schizophrenia, somatization disorders). Note: Follow-up by professionals will be offered when indicated. | inex_0260 | yes/no |
| 20 | Presence of other conditions or differential diagnosis better explaining the symptoms of the patient than the suspected ME/CFS, i.e., neuroendocrine diseases (such as thyroiditis or diabetes)  | inex_0270 | yes/no |
| 21 | Ongoing immunomodulatory or immunosuppressive therapy or prior treatment with Rituximab (anti-CD20- antibody).   | inex_0280 | yes/no |
| 22 | Clinical conditions that prohibit transitory volume changes or loss of plasma constituents other than Ig (e.g., serum albumin, electrolytes), equivalent to a plasma loss of about 10% per 1-fold processed plasma patient volume.       | inex_0290 | yes/no |
| 23 | Indications that prohibit anticoagulation using Heparin and/or Anticoagulant Citrate Dextrose (ACD-A) solutions  | inex_0300 | yes/no |
| 24 | Severe Hypercoagulability  | inex_0310 | yes/no |

|    |   |           |        |
|----|---|-----------|--------|
| 25 | Infection requiring hospitalization or intravenous administration of antibiotics/antimycotics or disease requiring administration of antivirus drugs (e.g., herpes zoster) within 4 weeks before starting the study treatment.  | inex_0320 | yes/no |
| 26 | Acute infection with Cytomegalie Virus (CMV) or Eppstein-Barr Virus (EBV)   | inex_0330 | yes/no |
| 27 | History of tuberculosis or evidence of active tuberculosis infection (positive QuantiFERON®-TB Gold Test).  | inex_0340 | yes/no |
| 28 | Tested positive for any of the following in the Screening Phase: Human Immunodeficiency Virus (HIV), hepatitis B virus surface antigen (HBs antigen), hepatitis B virus core antibody (HBc antibody), and hepatitis C virus. Note: Patients positive for anti-HBs after Hep B vaccination but negative for hBsAg and anti-HBc are eligible (Hepatitis B serology: Appendix II). | inex_0350 | yes/no |
| 29 | Positive SARS-CoV-2 PCR test result at screening or baseline visit  | inex_0360 | yes/no |
| 30 | Severe immune deficiencies (e.g., AIDS)   | inex_0370 | yes/no |
| 31 | Suspected allergies against camelid antibodies or agarose   | inex_0380 | yes/no |
| 32 | Pregnancy or breastfeeding at screening   | inex_0390 | yes/no |
| 33 | Vaccination with live vaccines within 12 weeks prior to randomization and during study participation until 12 weeks after completion of immunoabsorption treatment  | inex_0400 | yes/no |
| 34 | Non-live vaccination including vaccination against SARS-CoV-2 within 2 weeks prior to randomization and during the IA treatment period. Note: During the follow-up period, vaccination against SARS-CoV-2 will be allowed if in line with local regulations and if there are no concerns by the investigator.   | inex_0410 | yes/no |
| 35 | Positive serum alcohol test   | inex_0420 | yes/no |
| 36 | Positive test for drugs of abuse as per local standard at screening.  | inex_0430 | yes/no |
| 37 | Donation of blood over 500 mL or 200 mL of plasma within 3 months prior to screening  | inex_0440 | yes/no |
| 38 | Patient who has previously participated in this study and completed IA treatment  | inex_0450 | yes/no |
| 39 | Any comorbidity bearing risk that patient might not tolerate treatment as judged by investigator  | inex_0460 | yes/no |

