## 5 Analysis sets

### 5.1 Definitions

The modified **full analysis set (FAS)** consists of a modified intention-to-treat (mITT) population and will include all patients that were randomized and underwent at least one IA cycle (active or sham IA intervention).

The **per-protocol set (PPS)** comprises all subjects who completed five cycles of their assigned intervention (IA or sham IA) as planned and who completed the study without critical protocol deviations.

The **safety analysis set (SAS)** will include all patients that underwent at least one IA cycle (active or sham IA intervention). Patients will be analyzed according to the intervention they received.

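### Exclusion criterion 7 prints the white cell and platelet limits in a unit that makes them unusable as thresholds

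*SAP*

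**What the plan says.** Table 3 in Section 4.1 of the SAP lists the exclusion criteria, each tied to a yes/no variable. Criterion 7 (inex_0140) opens as a judgement criterion: "Clinically meaningful laboratory abnormalities at screening that would affect subject safety, as determined and documented by the investigator including but not limited to". Examples follow. The haematology examples are a haemoglobin limit, "Hemoglobin $< 8.0$ g/dL", then the white cell and platelet limits, "White Blood Cells count $< 2.5/\mu\text{L}$ or $> 12/\mu\text{L}$ , Platelet count $< 100/\mu\text{L". Liver limits as multiples of the upper limit of normal, a bilirubin limit in mg/dL and an INR limit come next. A closing note asks for values beyond the defined limits to be measured again before randomisation, to rule out laboratory error.

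Section 5.1 defines the per-protocol set as patients who had all five cycles as planned and "who completed the study without critical protocol deviations". It does not say which deviations are critical.

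**The concern.** A white cell limit of 12 per microlitre and a platelet limit of 100 per microlitre are far from any scale on which these counts are normally found. A threshold has to divide patients into those who meet it and those who do not, and as printed these do not.

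The criterion has a safety purpose. The procedure uses a peripheral venous access or a Shaldon catheter (Section 4), and criterion 23 refers to anticoagulation with heparin or a citrate solution. The closing note on repeat measurement also suggests that the numbers are meant to be used and are more than background. Anyone who checks eligibility against Table 3, whether at the site, in monitoring or in a deviation review, would have to replace the printed figure with one of their own.

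**Working it through.** **Inputs from the SAP (Section 4.1, Table 3, criterion 7).** White cells: lower limit 2.5/µL, upper limit 12/µL. Platelets: lower limit 100/µL.

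**Inputs that are assumptions.** The SAP gives no reference ranges. The check uses deliberately wide ranges: white cells 500 to 20,000/µL (usual adult about 4,000 to 11,000) and platelets 5,000 to 400,000/µL (usual adult about 150,000 to 400,000).

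The plan derives nothing from these limits, so there is no figure of its own to reproduce. The check is to apply each limit as printed.

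**White cells.** A patient meets the example if the count is below 2.5 or above 12. Ratio = count / 12.

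| Count per µL | Ratio to upper limit | Above 12? |
|---|---|---|
| 500 | 500 / 12 ≈ 42 | yes |
| 4,000 | 4,000 / 12 ≈ 333 | yes |
| 11,000 | 11,000 / 12 ≈ 917 | yes |
| 20,000 | 20,000 / 12 ≈ 1,667 | yes |

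The lower limit never comes into play: even 500 is 500 / 2.5 = 200 times it.

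**Platelets.** A patient meets the example if the count is below 100. Ratio = count / 100.

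| Count per µL | Ratio to limit | Below 100? |
|---|---|---|
| 5,000 | 5,000 / 100 = 50 | no |
| 150,000 | 150,000 / 100 = 1,500 | no |
| 400,000 | 400,000 / 100 = 4,000 | no |

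The answer is the same at both ends of each range, so it does not depend on where in the range a patient lies.

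**Is there another statement of these limits?** No other part of the SAP repeats them or gives a different unit.

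**Do the limits enter any estimate?** The full analysis set (Section 5.1) is defined by randomisation and at least one cycle, and eligibility is not part of it. The precision in Section 4.2 uses only a standard deviation of 5.8 and the group sizes (44 and 22, or 35 and 18 after drop-out). No blood-count limit enters either.

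**The case against.** The strongest reply is that this is an evident slip of notation that nobody would apply. Exclusion under criterion 7 turns on an abnormality that the investigator judges clinically meaningful and documents, and the numbers are open-ended examples. A patient with an ordinary white cell count would not be excluded, and one with a worrying platelet count still could be, under criterion 7 itself or possibly under criteria 8, 23 or 39. This stands. A reader might infer from the literal arithmetic that the plan excludes everyone, or that patients with low platelets are left unprotected. The wording of the criterion supports neither.

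A second reply concerns the per-protocol set. A reader might infer that wrong limits in inex_0140 carry through to that set and so to the sensitivity analyses. The SAP does not say that inex_0140 is re-derived from laboratory values, nor that an eligibility breach is a critical deviation. The route is possible but not stated.

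A third reply is that the unit may have been misread from the PDF. A single misread prefix letter in the unit would shift all three limits by the same factor, and superscripts in this text are not fully reliable: some B-cell markers in Section 7.3 carry a minus sign where the variable names in Table 5 suggest a plus. This cannot be ruled out. It is less likely than an error in the source, because the same unit appears three times while g/dL, mg/dL and the multiplication signs in the same criterion are intact.

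The reply does not remove the error. Judgement wording limits the harm of a wrong number, but the number is still printed as a limit, in a table that feeds a data field.

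**Conclusion.** The point holds as a wrong decision threshold in one table cell. As printed, essentially every white cell count is above the upper limit and essentially no platelet count is below its limit, on the assumption that the counts lie in the thousands and the hundred thousands per microlitre respectively. For usual adult counts the gap is about 333 to 917 times the white cell upper limit and 1,500 to 4,000 times the platelet limit. That pattern fits a missing multiplier or a wrong volume unit, but the SAP does not settle which.

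The consequence is limited. Investigator judgement prevents blanket exclusion, the primary analysis on the full analysis set and the stated precision are unaffected, and nothing in the SAP shows an effect on the per-protocol set. Because the criterion concerns patient safety and costs little to correct, it should be corrected all the same.

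**What to change.** Reconcile the unit of the three limits (two for white cells, one for platelets) with the protocol and with the unit in which the laboratory reports. Correct Table 3 before it is used to check eligibility or to flag deviations. The sponsor must confirm which limits apply; none is proposed here. If the protocol or the case report form carries the same text, correct it there too.

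The cost is one table cell in the SAP and a check of the source documents. No analysis, sample size or data collection changes.

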## 4.2 Power consideration

In this study, a total of 66 patients (allocated in a 2:1 ratio: immunoabsorption (IA) group: 44 patients vs. sham group: 22 patients) will be included. Limited data from 2 small pilot studies, investigating IA in 10 patients with CFS/ME, is available to date. Consequently, data is lacking about precise effects, clinical outcomes, and effect sizes in this group of patients.

The justification of the sample size is based on the primary endpoint (change from baseline of the Chalder Fatigue Scale). The Chalder Fatigue Scale measures fatigue in patients using the overall score (range from 0 to 33) derived from a questionnaire with 11 questions (each scored from 0 to 3, see (Cella & Chalder, 2010; Chalder et al., 1993) for more details). Based on Cella & Chalder 2010, the mean score in a population of patients

suffering from CFS is 24.4 (with a standard deviation of 5.8) and for a healthy sample a mean value of 14.2 (with a standard deviation of 4.6) was observed. A difference of 10 points cannot be expected in this study since only patients suffering from CFS are included. In the systematic review of Nordin et al. 2016 a minimal important difference for the global change ranges between 2.3 and 3.3.

In an earlier study (Cleare et al. 1999) examining the efficacy of various treatments for CFS/ME, the difference in means of the Chalder Fatigue Scale was 4.5 points (Likert score) between the active and the control group. However, no sham-controlled study evaluating the effect of IA on CFS/ME has been conducted so far, but first pilot studies suggest a positive effect of IA in patients with CFS/ME.

To explore the expected precision obtained from the planned study, the distance from the mean group difference of the primary endpoint (change from baseline in Chalder Fatigue Scale) to the limits is calculated using its 95% confidence interval (CI) and a common standard deviation of 5.8 as provided for patient with CFS/ME in (Cella & Chalder, 2010). Using these assumptions and the given group sample sizes of 44 patients and 22 patients, the distance from mean to the limits of the 95%-CI is 3.03 points in the Chalder Fatigue Scale. Assuming an expected drop-out rate of 20% (resulting in expected group sample sizes of 35 and 18 patients, respectively) the distance from the mean to the limits of the 95%-CI increases to 3.37 points in the Chalder Fatigue Scale.

## 5 Analysis sets

### 5.1 Definitions

The modified **full analysis set (FAS)** consists of a modified intention-to-treat (mITT) population and will include all patients that were randomized and underwent at least one IA cycle (active or sham IA intervention).

The **per-protocol set (PPS)** comprises all subjects who completed five cycles of their assigned intervention (IA or sham IA) as planned and who completed the study without critical protocol deviations.

The **safety analysis set (SAS)** will include all patients that underwent at least one IA cycle (active or sham IA intervention). Patients will be analyzed according to the intervention they received.

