After the last IA cycle, a blood sample for immunoglobulin titers is collected, the peripheral venous access (or Shaldon catheter) is removed and patients are discharged from the hospital if the investigator has no concerns. At EOT visit, patients will also complete the Chalder Fatigue Scale (Chalder et al., 1993), Fluge Score (Fluge et al., 2011; Fluge et al., 2015), and PEM questionnaires. In addition, patients will be instructed how to complete all of the requested questionnaires at home at follow up time points. If the IA treatments are performed according to the planned schedule, the end of treatment visit (EOT) will take place on Day 10. However, the EOT visit may vary between Day 9 and 12. If treatment needs to be terminated, the EOT can occur as early as day 2. In such cases, all examinations originally scheduled for day 10 will be conducted on the corresponding day. In addition, two of the four follow-up visits scheduled at month 2 (Day 60) and month 6 (Day 180; EOS, End of Study visit) will take place at the neurological wards and outpatient clinics respectively. Patients will be asked to bring all requested questionnaires (including Chalder Fatigue Scale), which they completed at home, to both follow-up visits, where further assessments and laboratory tests will be conducted. An optional second cerebrospinal fluid sample may also be taken on Day 60. The remaining two follow-up visits, scheduled at month 1 (Day 30) and month 4 (Day 120), will be conducted via telephone. During these visits, patients will be asked about any adverse events (AEs), concomitant medications, and questionnaires.

Figure 1 Schematic illustration of the study design

[figure not shown]

Table 1: Schedule of Assessments

| Period/Visit name  | SCR               | BL  | Treatment period (inpatient) |                 |                 |                 |                 |                 |                 |                 |     | Follow-up |                   |                  | EOS                |                         |
|--|-------------------|------------------|------------------------------|-----------------|-----------------|-----------------|-----------------|-----------------|-----------------|-----------------|-----|-----------|-------------------|------------------|--------------------|-------------------------|

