|  |                   |                  | 1                            | 2  | 3  | 4  | 5  | 6  | 7  | 8  | EOT | US        | 30 *6) | 60  | 120 *6) |                         |
| Study Days  | -42 to -21 | -20 to -1 |                              |                 |                 |                 |                 |                 |                 |                 |     |           |                   |                  |                    | 180 |
| Time windows (days)  |                   |                  |                              |                 |                 |                 |                 |                 |                 |                 |     |           | +/- 7             | +/- 7            | +/- 7              | +/- 7                   |
| Status  |                   |                  |                              |                 |                 |                 |                 |                 |                 |                 |     |           |                   |                  |                    |                         |
| Admission to hospital  |                   |                  | X                            |                 |                 |                 |                 |                 |                 |                 |     |           |                   |                  |                    |                         |
| Discharge from hospital  |                   |                  |                              |                 |                 |                 |                 |                 |                 |                 | X   |           |                   |                  |                    |                         |
| Discharge from study   |                   |                  |                              |                 |                 |                 |                 |                 |                 |                 |     |           |                   |                  |                    | X                       |

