### 5.2 Application

The primary analysis is performed using the full analysis set (FAS), including the estimated values from multiple imputations for missing values. An analysis of the primary outcome using the PPS is used as a sensitivity analysis. All safety analyses will be done using the SAS (Safety analysis set).

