## 7.2 Primary variable

The primary outcome variable is the Chalder Fatigue Scale (Chalder et al., 1993) (range 0-33) at day 60.

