### Clinical effectiveness related endpoints

- Chalder Fatigue Scale (Chalder et al., 1993) at End of Treatment (EOT) visit and at month 1, 4, and 6 after the completion of IA
- Post-COVID-19 Functional Status (PCFS) scale (Klok et al., 2020) at month 1, 2, 4, and 6 after IA completion (only in patients with PACS-CFS)
- the SF-36 physical domain (Ware & Sherbourne, 1992) at EOT visit and at month 1, 2, 4, and 6 after IA completion
- Fluge questionnaire (Fluge et al., 2011; Fluge et al., 2015) at month 1, 2, 4, and 6 after IA completion
- PEM frequency, strength and severity by PEM questionnaire (Cotler et al., 2018) at EOT visit and at month 1, 2, 4, and 6 after IA completion
- the Bell disabling scale (Bell, 1995) at EOT visit and at month 1, 2, 4, and 6 after IA completion
- the Compass-31 questionnaire (Sletten et al., 2012) at month 1, 2, 4, and 6 after IA completion
- Schellong Test (Fanciulli et al., 2019) at EOT visit and at month 2 and optional month 6 after IA completion
- hand grip strength test, at EOT and at month 2 and optional at month 6 after IA completion
- the 6 Minute Walking Test (6 MWT) ("ATS statement: guidelines for the six-minute walk test," 2002) at month 2 after IA completion
- optional neuropsychiatric assessment at month 2 after IA completion

- neurocognitive assessments (MoCA and SDMT) (Nasreddine et al., 2005) (Strober et al., 2020) at month 2 after IA completion
- quality of life (QoL) determined by the PROMIS questionnaire at month 1, 2, 4 and 6 after IA completion (Cella et al., 2019; Yang et al., 2019)
- PROMIS cognitive function short form 4a
- VLMT (verbal learning and memory test) (Helmstaedter et al., 2001)
- BVMT-R (brief visuospatial memory test revised) (Benedict, 1997)
- WAIS-IV (Wechsler adult intelligence scale) (Wechsler, 2008)
- TAP (Test of attentional performance) (Zimmermann & Fimm, 2004)
- LPS 50+ (Leistungsprüfungssystem (performance testing system) for 50 to 90 years old) (Sturm et al., 2015)
- TMT-A / B, Trail Making Test A / B (Reitan & Wolfson, 1993)
- RWT, Regensburger Wortflüssigkeits-Test (Regensburg Word Fluency Test) (Aschenbrenner et al., 2000)
- WST, Wortschatz-Test (Vocabulary test) (Schmidt & Metzler, 1992)

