### 9.2 Primary analysis

For the primary outcome, the Chalder Fatigue Scale at 2 months, descriptive statistics will be presented for both treatment arms. This will include the number of participants (n), mean, standard deviation (SD), median, interquartile range (IQR), minimum, and maximum for the continuous total score. Additionally, for the categorical responses (e.g., presence/absence of fatigue), frequencies and percentages will be reported.

Confirmatory analysis of the primary outcome will be conducted based on the full analysis set. An analysis of covariance (ANCOVA) will be conducted. The dependent variable is the Chalder Fatigue Score at day 60, independent variables include baseline Chalder Fatigue Score, treatment group (intervention / control), and age at baseline. The effect estimate for the treatment variable and the corresponding 95%CI will be reported. Sensitivity analysis will be done using the PPS without imputation of missing values.

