### 9.3 Secondary analyses

For all secondary endpoints, descriptive statistics will be calculated and presented at each time point of measurement for both treatment groups. For continuous secondary outcomes, this will include the mean, standard deviation, median, interquartile range, minimum, and maximum. For categorical or ordinal secondary outcomes, frequencies and percentages will be reported. These descriptive summaries will be presented in tabular format, and appropriate graphical representations, such as line plots for longitudinal data, bar charts, or box plots, will be utilized to visually depict trends, distributions, and differences between treatment arms across all assessment time points. For all secondary endpoints, analysis of

covariance (ANCOVA) models will be employed, analogous to the approach for the primary outcome. The choice of link function will be tailored to the specific nature of each outcome variable (e.g., linear for continuous outcomes, binary logistic for dichotomous outcomes, or ordinal for ordered categorical outcomes). In instances of repeated measures, mixed-effects regression models will be utilized, incorporating random intercepts for individual participants to account for within-subject correlation. Each model will include the respective baseline value of the endpoint, age at baseline, and treatment group as fixed effects. Effect estimates for the treatment variable, along with their 95% confidence intervals (CI), will be reported. All analyses will be conducted using the Full Analysis Set (FAS). Sensitivity analyses will be performed using the Per-Protocol Set (PPS), without imputation of missing values, to assess the robustness of the findings.

**Responder analysis:** Explorative analyses comparing responders and non-responders in both groups regarding PCS-associated signature at baseline: CD11c and IgM expression and an aCSM frequency. For this analysis a binary logistic regression model will be implemented with the responder (yes/no) variable as the dependent variable, the PCS-associated signature at baseline, the group and the interaction term between PCS-signature at baseline and group as independent variables.

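### The per-protocol set requires completion of a study that ends at Day 180, so the Day-60 sensitivity analysis drops valid scores because of later events

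*SAP*

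**What the plan says.** **Who is in the PPS.** SAP section 5.1 sets two conditions: five cycles of the assigned intervention, done "as planned and who completed the study without critical protocol deviations". Finishing the study is thus required in addition to finishing treatment.

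**When the study ends.** Section 4 describes the last visit as "month 6 (Day 180; EOS, End of Study visit". In Table 1 the row "Discharge from study" is marked only in the Day-180 column.

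**What the PPS is used for.** The primary variable in section 7.2 is the Chalder Fatigue Scale ("range 0-33) at day 60"). Section 5.2 says: "An analysis of the primary outcome using the PPS is used as a sensitivity analysis". Section 9.2 adds: "Sensitivity analysis will be done using the PPS without imputation of missing values". Section 9.3 extends this to the secondary endpoints: "Sensitivity analyses will be performed using the Per-Protocol Set (PPS), without imputation of missing values". Some of those are last measured at month 2, for instance the "optional neuropsychiatric assessment at month 2 after IA completion" in section 7.3.

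**Missing data.** Section 8 names the three missingness mechanisms, including missing not at random (MNAR). It plans 30 imputed data sets where missing at random (MAR) or completely at random is reasonable, and says that robustness will be examined. The analysis it specifies for that purpose is one on complete data without imputation.

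**The concern.** The outcome at Day 60 is fixed before anything that happens between Day 60 and Day 180. A rule that removes a patient from the Day-60 comparison for leaving on, say, Day 100 uses information from after the outcome. How the patient felt at Day 60, and the arm, may both influence that departure. A later protocol deviation would have the same effect if it were classed as critical.

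What is at stake is how the sensitivity analysis is read. A gap between the FAS and PPS results at Day 60 could come partly from who stays until month 6, which says nothing about the effect at Day 60.

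A second, smaller point concerns missing data. If dropout depends on the Day-60 score that was not observed, the imputed FAS analysis, the complete-data analysis and the PPS analysis can agree and still all be off. Their agreement cannot then support the robustness that section 8 sets out to examine.

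**Working it through.** **1. The SAP's own precision figures.** Inputs from section 4.2: SD 5.8; 44 and 22 patients; 35 and 18 after 20% drop-out. Half-width = t(0.975, n1+n2−2) × 5.8 × √(1/n1 + 1/n2).

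- 44/22: 1.998 × 5.8 × 0.2611 = 3.03 (SAP: 3.03).
- 35/18: 2.008 × 5.8 × 0.2900 = 3.38 (SAP: 3.37; unrounded 3.377).

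The figures reproduce and are not in dispute.

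**2. Precision cost of the Day-180 condition.** Section 4.2 does not say when the 20% drop-out occurs, so there are two readings. Both assume that nobody leaves the PPS for another reason.

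- *Loss by Day 60.* Then 35/18 have a Day-60 score, and the SAP gives no later loss. No later loss costs nothing. An assumed 5% of the 53 leaves 33/17, half-width 3.48 (cost 0.10). An assumed 10% leaves 32/16: 2.013 × 5.8 × 0.3062 = 3.57 (cost 0.20).
- *Loss by Day 180.* Then between 0 and 66 − 53 = 13 valid Day-60 scores are discarded. The half-width rises to 3.38 from somewhere between 3.38 and 3.03, a cost of 0 to 0.35.

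These use the unadjusted SD, as section 4.2 does. With an assumed baseline to Day-60 correlation of 0.5, ANCOVA shrinks them by √(1 − 0.25) = 0.866, so 0.35 becomes about 0.30.

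**3. Possible bias of the PPS estimate.** The SAP has no rate of loss after Day 60 and nothing on what drives it, so everything here is assumed. Simulation: 4,000 trials per case; 44/22; mean 24.4 and SD 5.8 from section 4.2; scores rounded and held to 0–33; correlation 0.5; ANCOVA on baseline and group. The probability of leaving after Day 60 is weighted by exp(z) of the Day-60 score, so a patient 1 SD worse is 2.7 times as likely to leave. Bias = PPS estimate minus the estimate from all Day-60 scores, as IA minus sham; a positive value counts against IA.

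| Loss after Day 60 | Bias (points) |
|---|---|
| None, or equal and equally dependent in both arms | about 0 |
| 5% IA, 10% sham | about +0.17 |
| 10% in both arms, half the slope in IA | about +0.15 |
| Sham only, 5 / 10 / 15 / 20% | +0.17 / +0.35 / +0.51 / +0.72 |
| IA only, 5 / 10 / 15 / 20% | −0.16 / −0.33 / −0.53 / −0.72 |

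With 5% loss in both arms and half the slope in IA, the bias is below 0.1. For sham-only loss of 10%, a correlation of 0.3 gives +0.42 and 0.7 gives +0.23. For scale, section 4.2 cites a minimal important difference of 2.3 to 3.3.

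**4. Do the specified sensitivity analyses relax MAR?** Complete-data ANCOVA is valid if missingness is unrelated to the Day-60 score given baseline score, age and group. The imputation model in section 8 may draw on all outcome variables plus age, sex and BMI. The complete-data analysis therefore makes a MAR-type assumption conditional on fewer variables, which is no weaker. The PPS without imputation adds further selection. Neither allows dropout to depend on the unobserved score.

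For scale, shifting the imputed scores of one arm moves the group difference by (missing share) × (shift), before scores are held to 33. At an assumed 20% missing in that arm, shifts of 2.3, 3.3 and 4.5 points give 0.20 × 2.3 = 0.46, 0.20 × 3.3 = 0.66 and 0.20 × 4.5 = 0.90 points.

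**The case against.** **Little rests on this set.** The primary analysis uses the FAS, and the complete-data analysis in section 8, if run on the FAS as its ordinary reading suggests, keeps every valid Day-60 score. A reader might infer that the primary result is compromised; the SAP does not support that. This stands, and it keeps the severity low.

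**The bias needs the arms to differ.** With equal and equally outcome-dependent loss it is about zero, and nothing in a double-blind sham design predicts loss in one arm only. This also stands. A reader might take 0.7 points as the expected error, but that is an extreme case with no support in the SAP.

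**FAS and PPS differ anyway** in treatment completion, deviations and imputation, so a gap between them never has a single cause. True, but those differences are intended features of a per-protocol analysis. Selection on what happens after the outcome is not.

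**Study completion may be defined in the protocol, and one PPS serves all endpoints.** The SAP does not define completion, and the protocol, which is not at hand, might. Within the SAP, however, Day 180 is the natural reading, and nothing cuts membership at Day 60. For month-6 endpoints the condition is not later than the outcome, which argues for a rule by endpoint. The point about later deviations holds only if such deviations are classed as critical.

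**Section 8 does not promise an MNAR analysis.** Correct. One might read the missing delta analysis as a broken commitment, but the text commits only to examining robustness. This part is an improvement, not an error.

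**Conclusion.** The PPS rule is wrong as written for the Day-60 primary endpoint and for endpoints last measured at month 2: it excludes valid outcome data because of later events. Severity is low, since only a sensitivity analysis is affected.

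No size can be taken from the SAP. The bias is about 0 if later loss is absent or alike in both arms. Under the assumed 2.7-fold dependence per SD, it is about 0.15 to 0.17 points with mild asymmetry and 0.2 to 0.7 in either direction only if loss of 5% to 20% is confined to one arm. The loss of precision is 0 to 0.35 points of half-width at the unadjusted SD of 5.8. The conclusion rests on reading study completion as reaching the Day-180 visit.

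The secondary point holds as a cheap improvement: the sensitivity analyses specified do not relax MAR.

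**What to change.** 1. **PPS by endpoint (section 5.1).** For endpoints up to Day 60, define the PPS as five completed cycles, an available Day-60 score, and no critical deviation up to and including the Day-60 assessment. Require later follow-up only for later endpoints. If completion to Day 60 was meant all along, one sentence saying so settles the matter.
2. **Delta-adjusted analysis (sections 8 and 9.2).** On the 30 planned imputations of the FAS, shift the imputed Day-60 scores separately in the IA and sham arms over a prespecified grid, held to 0–33. Report the estimate and 95% CI at each pair of shifts. Justify the range of the grid, for example against the minimal important difference of 2.3 to 3.3 and the 4.5-point difference cited in section 4.2.
3. **Clarification (section 8).** State that the complete-data analysis uses the FAS.

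The cost is two rules and one sentence in the SAP and a few lines of R, with no new data and no change to the primary analysis. The downside is a small amount of extra analysis and reporting. The changes should be made before unblinding.
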